During the Motor Battery assessments in the crossover, we will conduct Field Shaping Surveys to determine whether tailored activation of combinations of DBS contacts, guided by patient-specific network physiology, predicts changes in therapeutic window (the range of therapeutically effective stimulus amplitudes versus omnidirectional DBS). They will occur in the motor assessments at the conclusion of the first two crossover conditions. While in the operating room we will measure stimulus evoked activity and local field potential data through the DBS lead in response to hand, leg, and mouth movements. In addition to the primary study outcomes comparing directional versus omnidirectional DBS, we will use these encounters to determine if specific combinations of DBS contacts, guided by stimulus evoked activity and local field potentials in surgery, improve motor symptoms. Behavioral measures will include therapeutic window, MDS-UPDRS Part III, pegboard dexterity, gait speed test, and dynamic balance/posture measures (see motor battery above for descriptions) across different combinations of contacts on the segmented lead.

Non-motor assessments will occur on a different day and include patient-reported quality of life measures, cognitive/behavioral, and speech batteries (discussed previously). At study conclusion, we will conduct an open-ended exit interview to ask patients about their overall experience, to rank the programming strategies from the crossover study from best to worst, and explain their rationale for the rankings.

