Exploratory Crossover Arm Guided by Electrophysiology Biomarkers. These encounters and treatment assignments occur as part of research. Based on safety and tolerability testing from the field shaping survey, we will activate a combination of one or more DBS contact segments based purely on electrophysiology from the intraoperative assay over the next two months. Similar to the randomized crossover, participants will be allowed to adjust stimulus amplitude at home during the first month, within safety constraints defined by therapeutic window measures from the field shaping survey. They will remain on their preferred amplitude for the second month of the randomization period and then return at the end for motor and non-motor assessments. Motor outcomes for the crossover will include repeat UPDRS part 3, pegboard dexterity, gait speed test, and posture/balance measures from the Motor Battery (discussed previously). Non-motor assessments will occur on a different day and include patient-reported quality of life measures, cognitive/behavioral, and speech batteries (discussed previously). At study conclusion, we will again collect data regarding patient preference, ranking the various programming strategies from the crossover study from best to worst, and explain their rationale for their treatment preference.

Study Exit = visit with repeated outpatient EEG assay: This encounter will serve as a 1 year post-operative follow up visit that would normally be a part of routine care. We will repeat the Motor Battery at this time as well. To test the long-term robustness of our electrophysiological measures we will retest the electrophysiological assay conducted 1 year prior in the operating room, measuring cortical activation by DBS with EEG and 8 contralateral surface EMG

electrodes. We will not measure ECoG during this assay because this modality is only available during surgery (we remove the ECoG strip after testing in the OR). In this post-op visit, the implanted Boston Scientific pulse generator will provide the electrical stimulation. We will elicit cortical responses from stimulation from adjacent electrode contact pairs in a similar manner to our protocol during surgery. The total duration of the assay is approximately 30 minutes.

b. What is the probable length of time required for the entire study (i.e., recruitment through data analysis to study closure)?

5 years

c. What is the total amount of time each participant will be involved?

1 year

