and/or behavioral testing. Depending on potential attrition and AEs, this modest recruitment goal for early Y4 will provide flexibility to recruit additional participants to reach our goal of 30 participants for randomization, if necessary. Results will be recorded in a surgical implantation document including system tests showing normal DBS electrode impedances and side effect and efficacy thresholds during test stimulation. These data will be provided to NIH. To maintain blinding, patients will not be told which survey is being performed or which treatment condition they will receive.

Rationale: This is a minimum requirement to reach target of 30 participants implanted and randomized in the crossover by the end of Year 4 and will enable initial follow-up to be completed by Year 5.

Milestone 4.3: **Demonstrate changes in the therapeutic window using directional DBS and field shaping, guided by cortical activation patterns elicited by DBS during surgery (SAs 1.1, 1.2, 2.1, and 2.2).**

Success Criteria: Guided by cortical physiology elicited by DBS, demonstrate $\geq 20\%$ increase in therapeutic window in at least one grouping of 3 contact segments versus omnidirectional DBS in $\geq 40\%$ of the participants who have completed the field shaping survey by the end of Year 4. As per Milestone 2.4, we will classify all stimulation side effects by type (i.e., motor, sensory, oculomotor, ataxia, autonomic, etc.). The field shaping survey will be performed in conjunction with the assessment battery after the second treatment phase. To maintain blinding, patients will not be told which survey is being performed or which treatment condition they will receive.

Rationale: The Field shaping survey will evaluate the feasibility of using ECoG/EEG biomarkers to guide directional DBS activation and initiate the final crossover condition. This is a unique dataset that will link simultaneous EEG/ECoG activity elicited by directional DBS with the behavioral response to stimulation.

Milestone 4.4: **Safety Monitoring Committee will meet to discuss all AEs and SAEs at the end of Year 4.** This committee will also meet on an as-needed basis following SAEs to determine whether they are potentially study-related versus a known complication of DBS surgery.

Success Criteria: Meeting proceedings and decisions will be communicated to the PI and NINDS program officers.

Rationale: This process will ensure ongoing safety of the study.

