selected based cortical ERP physiology, using both therapeutic window and change in UPDRS part 3 as data nested within person. Secondary analyses will contrast the efficacy of these DBS adjustment strategies based upon changes in other elements of the Motor battery. In SA 2.3, we use the randomized, doubleblind crossover trial to compare changes in UPDRS and other measures of quality of life and motor, cognitive, behavioral, and speech function across the DBS programming strategies identified in SA 2.1. The primary statistical analysis will use Proc Mixed in SAS with active contact groupings including (1) conventional DBS, (2) multiple active contacts selected based on behavior, and (3) multiple active contacts based on ERPs as factor and patient preference and changes in PDQ-39 and UPDRS part 3 as data. Sample size for SA2. We will obtain multiple repeated measures within participants and can readily detect changes in patient preference, PDQ-39, UPDRS part 3, and other motor and non-motor variables of interest. Patient reported evidence for the hypothesis of superiority of current steering will be shown by determining that 20 or more of the 30 participants favor either current steering approach over conventional DBS using a binomial distribution based on patient preference (vote), PDQ-39, and UPDRS part 3. This would achieve a p value of < 0.049 . We will declare current steering DBS to be clinically superior to conventional therapy based on patient preference if 20 or more patients meet this criterion. We will measure the frequency by which current steering provides better outcomes versus conventional DBS, which could still be highly relevant and significant clinically (even if preferred by <20 participants). Secondary measures will quantify within-participant changes in upper limb dexterity, gait speed test, posture and balance, cognitive/behavioral measures, speech, and motor diaries. Additionally, we will contrast the probability that active contacts are shared among the programming strategies (conventional DBS, current steering guided by behavior, and current steering guided by cortical physiology). The extent to which contacts and stimulation parameters are shared among these approaches could be informative and provide a useful internal validation of the current steering approach.

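### The 20-of-30 preference rule has a 4.9% error rate only as a one-sided test of a single two-way comparison; counting either of two steering arms gives 9% to 58% if rankings are exchangeable

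*SAP*

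**What the plan says.** The rule is in the SAP under Sample size for SA2. Superiority is shown if "20 or more of the 30 participants favor either current steering approach over conventional DBS". The SAP says that this count will be judged "using a binomial distribution based on patient preference (vote), PDQ-39, and UPDRS part 3". The next sentence gives the error rate: "This would achieve a p value of < 0.049". The consequence is that steering is declared "clinically superior to conventional therapy based on patient preference if 20 or more patients meet this criterion". The SAP adds that the frequency of better outcomes with steering will be reported even if fewer than 20 prefer it.

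No null proportion, alpha or sidedness is given for this test. The only sidedness in the SAP is the two-sided 0.05 in the SA1 sample size. The SA1 text also says that the sample of 30 is driven by SA2.3.

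The SAP lists three groupings for SA2.3: conventional DBS, contacts chosen by behavior, and contacts chosen by ERPs. Two of the three are current steering. Protocol 16a collects preference in an exit interview by asking patients "to rank the programming strategies from the crossover study from best to worst". The Exploratory Crossover Arm text describes preference data being collected again, by "ranking the various programming strategies from the crossover study from best to worst".

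**The concern.** The stated p value belongs to a fair-coin null: one question, two answers. The counted event is different, because a participant has two ways to qualify (either steering arm) and one way to fail. Two chances against one generally raise the probability of qualifying when the strategies do not differ, and the SAP does not say how *either* is scored. The p value may therefore not describe the rule it is attached to.

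The rule carries an explicit declaration of clinical superiority, so its error rate should be known beforehand. Missing sidedness adds to the problem: a reader who carries over the two-sided convention from SA1 would believe the threshold meets 5% two-sided at 30 votes, and it does not. Nor is it stated how PDQ-39 and UPDRS part 3 enter a count that is then described as resting on preference.

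**Working it through.** **Inputs.** From the SAP: threshold 20, denominator 30, three strategies of which two are steering, stated p below 0.049. From Protocol 16a: preference is a ranking of the strategies. Assumed for steps 2 to 4: with no true difference all six orders are equally likely, and there are no ties.

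**1. Reproduce the stated figure.** One-sided exact tail at p0 = 1/2:

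P(X ≥ 20) = Σ C(30,k)/2^30 for k = 20 to 30 = 53,009,102 / 1,073,741,824 = 0.0494.

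Two-sided: 2 × 0.04937 = 0.0987. The normal approximation gives 0.034 one-sided without continuity correction and 0.050 with it; the mid-p value is 0.035. Only the one-sided exact tail matches. Since 0.0494 is not below 0.049, the sentence is also slightly wrong as written, which is a matter of rounding.

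**2. Null probabilities in a three-way ranking.** Let C be conventional, B behavior-guided and E ERP-guided. Of six orders, C is last in two (both arms above it), first in two (neither above it) and in the middle in two (only B above in one, only E above in the other).

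- P(B above C) = 3/6 = 1/2, and the same for E.
- P(at least one of B, E above C) = 4/6 = 2/3.

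**3. Each arm compared separately, success if either reaches 20 of 30.** The joint count over 30 patients uses cell probabilities 1/3 (both), 1/6 (B only), 1/6 (E only) and 1/3 (neither):

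P(B ≥ 20 or E ≥ 20) = 0.04937 + 0.04937 − P(both ≥ 20) = 0.09874 − 0.00777 = 0.0910.

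With a threshold of 21: 2 × 0.02139 − 0.00211 = 0.0407.

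**4. One pooled count, a participant qualifying if at least one arm is above C.** The expected null count is 30 × 2/3 = 20, which is the threshold itself. P(X ≥ 20 | 30, 2/3) = 0.585. Holding one-sided 5% on this reading needs 25 of 30 (0.035), as 24 gives 0.084.

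| Scoring of the rule, 20 of 30 | False-positive rate |
|---|---|
| One two-way comparison | 4.9% |
| Each steering arm separately, either suffices | 9.1% |
| Pooled, at least one arm above conventional | 58% |

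**5. Fixed count of 20 when votes differ from 30 (p0 = 1/2).**

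| Votes | One-sided | Two-sided | Smallest one-sided 5% cut-off |
|---|---|---|---|
| 27 | 0.0096 | 0.019 | 19 |
| 28 | 0.018 | 0.036 | 19 |
| 29 | 0.031 | 0.061 | 20 |
| 30 | 0.049 | 0.099 | 20 |
| 31 | 0.075 | 0.150 | 21 |

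**6. Power at an assumed true pairwise preference of 75%, 30 votes.** Threshold 20: 0.894. Threshold 21: 0.803.

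**The case against.** **The p value itself points to a two-way null.** It reproduces only at p0 = 1/2, so the authors probably had a steering-versus-conventional vote in mind. A reader might infer from the three-way ranking that p0 = 2/3 and that the error rate is therefore 58%. The documents do not support that as a fact. It needs both the pooled reading of *either* and exchangeable rankings without ties. If patients always placed the two steering arms on the same side of conventional DBS, every reading would return to 4.9%.

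**The design may not be a three-way randomization.** Protocol 16a (Crossover Study) and the SAP describe three randomized conditions. Protocol Table 3 shows a randomized crossover of two conditions followed by a separate crossover to EEG/ECoG-guided stimulation. Protocol 16a and 16d label that arm exploratory, and Milestones 2.6 and 4.3 treat it as the final one. If it always comes last, exchangeability has no design basis, and neither 9.1% nor 58% is exact. This stands. It limits how firmly the two figures can be stated, but it does not supply the missing null.

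**The rule is not the primary analysis.** The SAP's primary analysis of SA2.3 is a mixed model, so a reader should not infer that it fails with this rule. The superiority declaration is nevertheless tied to the count.

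**One-sided testing is legitimate** for a directional hypothesis. The gap is the missing label. Nor is it true that the count of 20 meets 5% only one-sided: at 28 or fewer votes it meets 5% two-sided as well (0.036 at 28).

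**The denominator is a small matter.** The SAP names 30, and Milestone 4.2 keeps recruitment flexible "to reach our goal of 30 participants for randomization". Enrollment of up to 40 (Protocol 15a) does not mean 40 votes. The fixed count is too lenient only above 30 and errs on the safe side at 28 or fewer.

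**Conclusion.** The point holds as a specification fault with a measurable consequence. The SAP attaches to its superiority threshold an error rate that is correct for a single two-way comparison tested one-sided with 30 votes, while its wording describes an either-of-two criterion. The false-positive rate is 4.9% for a single comparison, 9.1% for separate comparisons and 58% for a pooled count. The last two figures assume exchangeable three-way rankings without ties. The documents do not settle which scoring applies, so the range is the finding and no single value in it should be quoted as the plan's error rate.

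A reader might also infer that keeping the pooled definition and testing it against 2/3 must be ruinous, because 25 of 30 has only 20% power at a true 75% either-arm preference against 80% for 21 of 30 at a true 75% pairwise preference. Those are different quantities. Under a Plackett-Luce ranking model (an assumption) with each steering arm beating conventional 75% of the time, the weights are 3, 3 and 1, either-arm preference is 6/7, and 25 of 30 has 75% power. The pairwise definition is preferable because its null is clear, not because of that contrast.

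**What to change.** In the SAP, Sample size for SA2:

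- Define success as one pairwise comparison: the behavior-guided steering arm ranked above conventional DBS. Randomized order supports a null of 1/2 for this pair. It does not do so for the ERP-guided arm if that arm always comes last.
- Reconcile Protocol 16a (Crossover Study) and the SAP with Protocol Table 3 and the Exploratory Crossover Arm text on whether the ERP-guided arm is part of the randomization.
- State a one-sided exact binomial test of 1/2 at 0.05, with the cut-off read from the number of patients who give a vote: 20 of 30 (0.0494), 20 of 29, 19 of 28 or 27, 21 of 31 (0.035).
- Replace the stated p value with: below 0.05, one-sided.
- Report the proportion with an exact 95% confidence interval. For 20 of 30 this is 0.472 to 0.827, which includes 1/2, so the one-sided label must be visible beside it.
- Say whether PDQ-39 and UPDRS part 3 enter the criterion and, if so, how.
- If both steering arms are to be tested, require 21 of 30 for each (one-sided 0.021 each; 4.1% overall under exchangeable rankings).

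**Cost.** The single comparison changes wording only: the threshold at 30 votes is unchanged, and the exit ranking already supplies the data. Testing both arms raises the threshold by one patient and lowers power at a true 75% pairwise preference from 89% to 80%.

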Quality of life battery											
Speech battery											
Field shaping survey											
PRISMA MRI with tractography											
ERP assay (EEG/ECoG/EMG)											
O-arm CT for lead localization											
Routine post-op CT brain											

Exploratory Crossover Arm Guided by Electrophysiology Biomarkers: In this nested arm of the crossover study, we will activate a combination of one or more DBS contact segments based purely on electrophysiology from the intraoperative assay. It will involve two study visits over the course of 2 months. For this condition we will assess our motor battery in one visit (see 16a above) lasting approximately one hour and our cognitive/speech/quality of life batteries (see 16a above) in one visit lasting approximately 3 hours.

Study Exit visit: This portion of the study will involve a single visit to serve as a 1 year post-operative follow up to evaluate the long term robustness of our electrophysiological measures. We will reassess portions of our motor battery (see 16a above) and our ERP assay. This visit should last less than 2 hours.

e. List the procedures, the length of time each will take, and the frequency of repetition, and indicate whether each is done solely for research or would already be performed for treatment or diagnostic purposes (routine care) for the population. *Insert additional table rows as needed.*

Please see table 3 above for frequency of repetition. Each measure will be assessed once at each indicated visit.

Procedure	Length of Time Required of Participants (minutes)	Frequency of Repetition	Research (Res) – OR- Routine Care
Measures acquired during DBS surgery			
Intra-op ERP assay	≤30	1 repetition	 Res  Routine
Intra-op O-arm CT	10		 Res  Routine
Post-op brain MRI	30		 Res  Routine
total time (beyond routine care)	≤30		
Motor battery			
UPDRS-part 3	5	7 repetitions (pre-op; monopolar)	 Res  Routine
Therapeutic window	30		 Res  Routine

Activities-specific balance confidence (ABC) scale	3	survey; cross-over visits 4a, 5a, and 6a)	 Res  Routine

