Rationale: Measured routinely in the monopolar survey, therapeutic window is defined as the current difference between the thresholds for efficacy and adverse stimulation effects for each contact on the DBS electrode array. One goal of directional DBS is to increase the size of the therapeutic window versus omnidirectional stimulation within individuals. Based on multiple publications, directional DBS is very likely to accomplish this. Using the criteria proposed above, Stiegerwald et al recently showed a 31% median improvement in therapeutic window and greater than 20% improvement in at least one contact in 9 of 11 patients (81%). Based on their data, we believe that our 40% success criterion is conservative, not only relative to their early results, but also given that improvement in 40% of patients (or even less) might still be a clinically important difference. In an unlikely scenario where there is no change in the floor of the therapeutic window, or it occurs relatively infrequently (in <40% of participants), we could still proceed with the randomized crossover, as proposed in SA2.3, instead selecting contacts based on therapeutic window size or percent change in UPDRS subscore for the stimulated side of the body, rather than therapeutic window floor. Field shaping with multiple active contacts on the novel DBS lead still might be preferred by patients based on activating larger tissue volumes in the STN region, regardless of whether directional stimulation alters therapeutic window floor. This option would be discussed and negotiated with NIH staff to explore this possibility based on the available data at the time.

Milestone 2.5: **Characterize changes in ERPs measured by EEG/ECoG with directional stimulation during DBS surgery.**

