SA1. To test the hypothesis that specific contacts on a novel segmented DBS lead in the STN region activate functionally distinct populations of cortical axons within individual PD patients. SA1.1 will measure within-participant contrasts in therapeutic window and UPDRS part 3 change versus pre-op baseline across the different segments on the directional DBS lead with two-way repeated measures mixed models using Proc Mixed in SAS, with conventional versus current steering DBS contacts as factors and therapeutic window and change in UPDRS part 3 as data. The primary outcome measure for SA1.2 will compare whether intraoperative ERPs predict within-participant changes in the clinical outcomes from SA1.1. We will contrast the ERPs within and across stimulation sites with two-way repeated measures mixed models using Proc Mixed in SAS, with stimulus amplitude, location, and recording modality (EEG or ECOG) as factors and P1/N1 latency and HFO integrated area as data. Using linear contrasts from the regressions, we will directly compare whether EEG and ECOG measures of DBS amplitude thresholds (1) that change P1/N1 latency and (2) elicit the large amplitude HFOs better predict the size of the therapeutic window for a given DBS electrode contact. Secondary outcomes will correlate these amplitude thresholds with changes in the UPDRS part 3 score, UPDRS subscores, and other elements of the Motor battery measured in SA1.1. To control for potential subclinical corticospinal tract activation, we will report the latency and magnitude of EMG response(s) in the contralateral arm and leg muscles using residual analyses, when and if these responses are present. Sample size for SA1. Our preliminary findings show robust within- and between-subject changes in ERP latency that predict postoperative motor side effects. For the first primary outcome, a sample size of 18 will have 80% power to detect a difference between a null hypothesis regression slope of 0 and an alternative regression slope of 0.3 or higher standardized units, assuming that the standard deviation of the predictor variable, DBS amplitude threshold, is 2.370 mA (the standard deviation of the stimulus intensities) and the standard deviation of the normalized residuals ($sd=1$) of the therapeutic window using a t-test with a 0.05 two-sided significance level. Thus, we will be overpowered for SA1, because a large sample of 30 is dictated by SA2.3. As an additional secondary analysis, we will compare the predictive power of EEG versus ECOG, we will first regress the primary outcomes on EEG and then determine how much of the residual variance is explained by ECOG. If EEG explains 50% of the variance in the primary outcome, then we will have 80% power to detect an increase in the R-square of 8.6%. If the additive R-square of EEG is 25%, we will have 80% power to detect an increase of 12.9%. If we cannot demonstrate superiority of ECOG, we would default to the less invasive modality. We will look at the assumptions of the model by examining the residual plots in the regression models for both modalities.

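### The SAP invites a claim of clinical significance below its 20-of-30 criterion, from a frequency of better outcomes that has no chance reference

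*SAP*

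**What the plan says.** The SAP (Statistical Analyses, Sample size for SA2) bases its preference claim on "20 or more of the 30 participants favor either current steering approach over conventional DBS using a binomial distribution", and adds: "This would achieve a p value of < 0.049". The decision rule follows: "We will declare current steering DBS to be clinically superior to conventional therapy based on patient preference if 20 or more patients meet this criterion".

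The next sentence introduces a second measure: "We will measure the frequency by which current steering provides better outcomes versus conventional DBS". Its closing clause then tells the reader how a result short of the threshold may be viewed: "which could still be highly relevant and significant clinically (even if preferred by <20 participants").

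Neither document gives this second measure a cut-off, a minimum difference on PDQ-39 or UPDRS part 3, a null proportion, a test or an interval. Neither says how patients who do worse, or who are tied, will be shown.

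The Protocol (Item 16.a, Crossover Study) gives each of the three strategies one two-month period. On the assessments, Item 16.e says: "Each measure will be assessed once at each indicated visit". Preference is collected as a best-to-worst ranking of the strategies at study conclusion.

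**The concern.** A count of patients who did better in one period than in another has a large expected value even when the treatments are identical. Each strategy is given once and each measure is taken once per visit. A patient's better PDQ-39 or UPDRS part 3 score on steering therefore cannot be separated from ordinary variation between visits. Without the matching count of patients who did worse, and without the value expected by chance, a reader cannot tell a real benefit from noise.

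The clause sits directly after the decision rule and provides favourable language for a result that misses it. A report that follows the SAP to the letter could describe a chance-level count as clinically significant.

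**Working it through.** **Inputs.** There are 30 participants (SAP, Sample size for SA1: "a large sample of 30 is dictated by SA2.3"), a threshold of 20, and three conditions, one conventional and two steering (SAP, SA2.3). The shares below assume no true effect, exchangeable conditions and no ties. The documents set no tie rule.

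**1. The SAP's own p value.** For X ~ Binomial(30, 1/2), P(X ≥ 20) = 0.0494, which is 0.049 to three decimals. Read literally, the stated bound is missed by 0.0004. The two-sided exact value is 0.0987. The SAP figure is thus a one-sided exact test against a null share of one-half.

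**2. Share better on steering by chance.**
- One given steering arm against conventional: 1/2, or 30 × 1/2 = 15 patients. The central 95% range of Binomial(30, 1/2) is 10 to 20.
- The better of the two arms against conventional: conventional is best of three with probability 1/3, so the share is 1 − 1/3 = 2/3, or 20 patients. The central 95% range of Binomial(30, 2/3) is 15 to 25.

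Simulation with within-patient correlations of 0, 0.5 and 0.9 gave 0.50 and 0.67 each time. An uninformative ranking of three strategies gives the same two shares, so the preference vote is covered without a model of visit noise.

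**3. Share better when steering is slightly worse.** Suppose both steering arms are worse by 0.2 SD of single-visit noise (an assumption, for illustration), with independent normal noise.
- One arm: Φ(−0.2/√2) = Φ(−0.141) = 0.44.
- At least one arm: 1 − ∫ φ(x) Φ(x + 0.2)² dx = 0.61.

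**4. What counts below 20 can show.**

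| Count of 30 | Share | Exact 95% interval |
|---|---|---|
| 15 | 50% | 31–69% |
| 19 | 63% | 44–80% |

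Both intervals contain one-half, and both contain two-thirds (66.7%). A count of 15 to 19 has probability 0.52 under a share of one-half and 0.40 under two-thirds.

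**5. The threshold when either arm counts.** For X ~ Binomial(30, 2/3), P(X ≥ 20) = 0.58. At one-sided 0.05, this null share would need 25 or more (P = 0.036; 24 or more gives 0.084).

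**The case against.** The strongest defence is that the clause decides nothing. It says the frequency could be relevant, and superiority is still declared only at 20 or more. The Protocol (Item 23, Milestone 1.2) describes a feasibility study, where descriptive frequencies are normal. Benefit in a minority can matter clinically, since ring-mode settings stay available to those who prefer them. The SAP's primary analysis is the mixed model, which would tend to show harm if steering were worse. All of this stands. It limits the point to the interpretation of one frequency, but does not supply the missing reference value, and the SAP does not tie that frequency to the model.

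Three stronger readings are tempting but not supported.
- A reader might infer that no result can count against steering. In fact, 19 or fewer means superiority is not declared.
- A reader might take the Protocol's remark that "improvement in 40% of patients (or even less) might still be a clinically important difference" as a 40% floor for the crossover. It belongs to Milestone 2.4, on therapeutic window at the monopolar survey. That is a different outcome and visit, with its own 20% minimum change.
- A reader might say that a count of 12 to 19 arises in 85% of trials with no effect. That holds only at a null share of one-half. At two-thirds it is 41%, and the documents define no such band.

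The two-thirds share also depends on carrying the either-arm wording of the preceding rule into a sentence that says only current steering. If one arm is meant, the reference is one-half.

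**Conclusion.** The concern holds as a point about interpretation. The decision rule is intact, but the clause after it permits a statement of clinical significance from an uncalibrated frequency. With no effect, that frequency is expected to be 50% for one arm and 67% for the better of two. With a small disadvantage of 0.2 SD it would still be about 44% and 61%.

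The no-effect shares assume exchangeable conditions and no ties. Ties would lower both. Counting a patient as better on any one of the three outcomes would raise them.

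The calculation also shows that restating 20 as the cut-off is not enough. It is calibrated for one steering arm against conventional, not for a patient favouring either of two.

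**What to change.** 1. Delete "which could still be highly relevant and significant clinically (even if preferred by <20 participants" with its closing bracket, and label the frequency descriptive.
2. For each steering arm separately against conventional, tabulate the numbers better, worse and tied. Give the exact 95% interval for the share better among non-tied patients, shown against one-half.
3. State that superiority is not shown if the preference criterion is not met.
4. State that any claim of benefit on PDQ-39 or UPDRS part 3 rests on the primary Proc Mixed contrasts with 95% confidence intervals.
5. Apply the preference criterion per steering arm. Say which arm carries the claim or how the two tests are combined, since two tests at 0.0494 have a joint error of up to 2 × 0.0494 = 0.099.

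The cost is SAP wording and one added table, with no new patients, visits or data. The sponsor gives up a favourable reading of a failed criterion and the easier either-arm count.
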